4 DEFINING PRESYNCOPE AND SYNCOPES

4.1 Presyncope

For this study, the case definition of presyncope was based on review of the literature, an amended Blood Donations Reactions Inventory (BDRI) which was used in previous studies including the CISA Hydration Study, expert opinion, and prior experience with the CISA hydration study.¹²⁻¹⁴ Although there may be measurable physiological changes with presyncope (e.g., decrease in heart rate or blood pressure), there are no established cut-offs that define presyncope. Therefore, the case definition is based on subjective criteria. The case definition previously used in CISA hydration study to Prevent Post-Vaccination Presyncope (“Water and Vaccines Study”) is outlined below and will be used as the primary definition of presyncope in this study:

Primary definition: *Sudden onset of one or more of the following symptoms (reported as “a little bit”, “somewhat” or “a lot”) or signs during the post-vaccination observation period in the clinic:*

Symptoms

- Feeling like you might “pass out” or faint
- Feeling dizzy, like the room is spinning
- Feeling weak
- Feeling like your face is getting red and warm (or hot), like blushing or flushing
- Noticing any change in your vision, like spots or flickering lights, tunnel vision, or loss of vision
- Experiencing ringing in your ears, decreased hearing, or sounds seem far away
- Feeling lightheaded
- Feeling like your heart is beating fast or hard or pounding
- Feeling hot or sweaty
- Feeling cold or “clammy”
- Feeling like you are breathing fast or hard
- Feeling like you might throw up (nausea)

Signs

- Pallor
- Sweatiness
- Facial flush
- Decreased interactivity (decreased level of arousal or responsiveness)

AND

- Not syncope
- Not due to another cause
- Not clearly present at baseline

In exploratory analyses we will employ two alternate case definitions for presyncope.

Alternate definition 1: *Sudden onset of one or more of the above symptoms (reported as “somewhat” or “a lot”) or signs during the post-vaccination observation period in the clinic.*

Alternate definition 2: *Sudden onset of one or more of the following symptoms limited to feeling like you might pass out, dizziness, weakness, or lightheadedness symptoms (reported as “a little bit”, “somewhat” or “a lot”) or signs during the post-vaccination observation period in the clinic.*

4.2 Syncope

Syncope (fainting) that occurs in an otherwise healthy person after receipt of a vaccine or during venipuncture is usually attributed to vasovagal syncope, and may occur alone (simple syncope) or may be associated with tonic-clonic movements (convulsive syncope, anoxic seizure).^{12,13} For the purposes of this study, we have defined syncope as: *Any sudden and brief loss of consciousness or postural tone after vaccination from which recovery is spontaneous and is not attributed to another cause (e.g., anaphylaxis).* For purposes of this study, cases counted as syncope must occur during the post-vaccination observation period.

Usual clinical care will be provided to any subject who develops syncope.

5 STUDY DESIGN

This study is a prospective, randomized clinical trial that will be conducted in adolescents (10 through 14 years of age) receiving at least one recommended intramuscularly administered vaccine to evaluate the efficacy and acceptability of using two different, simultaneously administered interventions that might prevent post-vaccination presyncope, and by extension syncope. The two interventions to be evaluated together are Buzzy®, which is a medical device designed to reduce vaccination pain, and an electronic game. We will evaluate both interventions when administered simultaneously (Buzzy® and electronic game). We will enroll approximately 340 subjects into this study. Eligible adolescents will be randomized (1:1) to either the intervention or control group: 1) intervention (Buzzy® and electronic game); or 2) control (usual care) to assess for acceptability and efficacy. Detailed data will be collected and described from study participants including demographics, medical history, baseline anxiety, and needle phobia. Participants will be observed for 20 minutes following receipt of vaccines and reassessed for post-vaccination anxiety, immediate and subsequent post-vaccination pain (within 1 minute and at 10 minutes), and the occurrence of witnessed syncope or presyncope, and presyncope symptoms as rated by the modified BDRI. For the primary objective, we will assess the efficacy of the intervention to decrease presyncope symptoms or signs as compared to usual care. For the secondary objectives we will assess the pre- and post-vaccination anxiety score, the immediate post-vaccination injection-site pain score, and the acceptability of the intervention. For the exploratory objectives we will assess the efficacy of the intervention to decrease presyncope symptoms or signs as compared to usual care using alternate case definitions for presyncope and we will assess factors associated with post-vaccination presyncope.

6 STUDY ENROLLMENT AND WITHDRAWAL

Subject Inclusion and Exclusion Criteria will be reviewed at Visit 1 to assess eligibility for study participation.

6.1 *Subject Inclusion Criteria*

Subjects who meet all of the following criteria will be eligible to participate in this interventional study.

1. 10 years through 14 years of age
2. The subject must be receiving at least one vaccine delivered intramuscularly
3. The parent/guardian must be willing and capable of providing written informed consent for the adolescent and the adolescent must be willing and capable of providing assent.
4. The subject must be willing to stay for the completion of all study-related activities.
5. Parent/guardian and adolescent must speak and read English by self-report
6. Parent/guardian must be willing to let their child select an electronic game to play during the study

6.2 *Subject Exclusion Criteria*

Subjects who meet any of the following criteria will not be eligible to participate in this study:

1. Receipt of investigational or experimental vaccine or medication within the previous two weeks
2. Receipt of routine injectable medication
3. Permanent indwelling venous catheter
4. Blood drawn within the past hour or scheduled for a blood draw during the post-vaccination observation period
5. Injection of medication during the past hour or scheduled for injection of medication during the observation period.
6. Cold intolerance or cold urticaria
7. Raynaud's phenomenon
8. Sickle cell disease
9. Significant visual impairment or blindness
10. Significant auditory impairment or deafness
11. Febrile(>38.0°C) or acutely ill individuals
12. Upper arm or shoulder pain or injury
13. Has the subject had video game-induced seizures?
14. Adolescent or parent/guardian is an immediate relative of study staff or an employee who is supervised by study staff.
15. Any condition that would, in the opinion of the site investigator, place the participant at an unacceptable risk of injury or render the participant unable to meet the requirements of the protocol

6.3 *Recruitment*

The 340 participants in this study will be male or female adolescents 10 to 14 years of age. Adolescents will be recruited from designated study sites affiliated with the Duke University Health System (Duke Children's Primary Care, Durham Pediatrics, and

Regional Pediatrics). Adolescents will primarily be recruited at the time of well child visits.

6.4 Reasons for and Handling of Withdrawals

The following may be reasons for study withdrawal:

- As deemed necessary by the principal investigator (PI).
- Parent(s)/Legally Authorized Representative(s) (Guardian(s)) withdrawal of permission for their adolescent to participate.
- Termination of the study by the sponsor.

A parent/guardian may withdraw permission for their adolescent to participate at any time and for any reason, without penalty. Subjects who are withdrawn from the study after receiving intervention will not be replaced. For subjects who received intervention, data collected prior to withdrawal in the study will be included in the study.

6.5 Termination of Study

This study may be terminated for safety concerns of the principal investigators from the research site, CDC, or participating Institutional Review Board (IRB).

7 STUDY SCHEDULE, PROCEDURES, & EVALUATIONS

7.1 Schedule of Events

Adolescents meeting the proposed eligibility criteria will be recruited and if enrolled the subject could spend up to two hours in the clinic. Written permission for the adolescent to participate will be obtained from parent(s)/guardian(s) prior to conducting any study procedures. Written or verbal assent, depending on the age of the adolescent, will also be obtained. **Table 1** describes the proposed schedule of study visits.

Table 1: Schedule of Study Events:

Procedure	Pre-Vaccination Day 1	Vaccination Day 1	Post-Vaccination Day 1
Informed consent / Assent	X		
Inclusion/Exclusion	X		
Demographics	X		
Medical history	X		
Concomitant medications	X		
Beverage and food intake assessment on day of vaccination	X		
PROMIS Pediatric Anxiety Short Form	X		
Needle phobia assessment	X		
State Anxiety assessment	X		X ¹ (20 minutes)
Record/obtain physical measures (height and weight) and vital signs (blood pressure and pulse and baseline pain assessment done per usual care)	X		
Randomization	X		

Simultaneous Buzzy® and electronic game intervention or usual care	X		
Administer vaccines (not a study procedure)		X	
Injection site pain assessment			X (within 1-3 and at 10 minutes)
Presyncope symptoms assessment			X (15 minutes)
Acceptability Assessment			X (20 minutes)

¹ Complete prior to acceptability assessment

Visit 1, Study Day 1 Clinic Visit Prevaccination Assessments

- Obtain parent(s)/guardian(s) permission by written informed consent
- Review and confirm study eligibility (Section 4.1 and 4.2)
- Obtain medical history
- Obtain demographic data
- Obtain concomitant medication use within one week of enrollment
- Record height and weight and vital signs (blood pressure and pulse) from the medical record. Obtain measures if not already taken and recorded at clinic intake. Record baseline pain assessment if determined as part of clinical care
- Complete beverage and food intake assessment for the day of vaccination
- Complete the needle phobia assessment
- Complete the general anxiety assessment and the state anxiety assessment
- Randomize study participant to one of the two study arms
- Administer assigned study intervention if randomized to that group

Visit 1, Study Day 1 Clinic Visit Vaccination

- Vaccines administered by clinic staff (Not a study procedure)
- Vaccines administered as usual care will be recorded by study team

Visit 1, Study Day 1 Clinic Visit Post Vaccination Assessments

- Complete the Wong-Baker Faces Pain assessment for **each arm** an injection is given in (immediately after withdrawal of the needle after the last vaccination within 1 minute (up to 3) after last injection and at 10 (up to 15) minutes after the last vaccination). If multiple injections are given in the same arm only 1 Wong-Baker Faces Pain assessment will be performed for that arm at 1-3 minutes and 10 (up to 15) minutes after the last injection.
- Complete the presyncope symptoms assessment modified BDRI (15 (up to 20) minutes post vaccination)
- Complete the state anxiety assessment (20 [up to 25] minutes post vaccination)
- Complete the acceptability assessment (20 [up to 30] minutes post vaccination)

7.2 Parent/Guardian(s) Permission Process (Informed Consent)

The consent/assent process will take place in research or clinic exam rooms behind closed doors to assure privacy of the prospective participant. Study staff will be available to answer all parent/adolescent questions before and after permission is obtained. After initial discussion of the study, parent(s)/guardian(s) will be given as

much time as needed to decide whether or not to give permission for their child to participate in this study. We anticipate that the initial consent/assent discussion, including presenting the information in the consent/assent document and answering questions will take about 30 minutes. During the consent/assent process, it will be stressed that participation is voluntary and that parents can withdraw permission for their adolescent to participate at any time. Permission will not be obtained from parent(s)/guardian(s) who do not read, who are blind, or who do not read/understand English. Parent(s)/Guardian(s) will be given a copy of the signed informed consent to take home with them. The original copy of the consent/assent will be kept in the study records and a third copy will be included in the adolescent's medical record per local requirements. Eligibility of the adolescent will also be assessed.

7.3 Overview of Study Assessments

Table 2 briefly outlines factors of interest that are potentially associated with pre-syncope or syncope. A more complete description of some of the specific measurements and questionnaires follows the table.

Table 2: Factors of Interest that are Possibly Related with Pre-syncope or Syncope		
Domains of Interest	Source of Information	Information obtained
Demographics	Participant and/or parent report	Participant's gender, age, race, ethnicity
Underlying Health (Chronic or acute illness)	Participant and/or parent report Review of medical record	Medical history information: (history of pre-syncope, syncope, cardiac conditions, seizures, hypoglycemia, diabetes, prescription and over-the counter medications in preceding week, supplements in preceding week)
Physical Measures	Height, weight, pulse rate and blood pressure measurements (from medical record if obtained or measured, otherwise measured by study staff) Pain at baseline (from medical record)	Height, weight and calculated BMI Pulse rate and blood pressure Pain assessment at baseline
Fatigue/ tiredness	Participant response	Estimated hours of sleep the previous night Feeling tired
Hunger	Participant response	Last food eaten Hunger estimation
Thirst	Participant response	Time/type of last beverage consumed prior to vaccination

		Quantification of last beverage Thirst estimation
Needle-related fear	Participant response	Needle phobia questionnaire Global question about fear of injections
Anxiety	Participant response	PROMIS Pediatric Anxiety Short Form pre-vaccination, and state anxiety questionnaire pre- and post-vaccination
Number of Injections	Medical record review (EHR/electronic health record or State Immunization Registry)	Number / name / site of injections administered in clinic
Pain	Participant response	Wong-Baker Faces Pain Scale score post vaccination
Past history of presyncope or syncope after injection or blood draw during the past 5 years	Participant response	Questions about past history of almost fainting or fainting and circumstance

7.4 Demographic Information, Medical History

The participant's gender, age, and race/ethnicity will be obtained from parent/guardian report at the time of enrollment. The participant's medical history including: history of pre-syncope, syncope, cardiac history, seizures, hypoglycemia, diabetes, prescription and over-the counter medications in the preceding week, and supplements in the preceding week will be obtained by review of the electronic health record (EHR) and will be reviewed and confirmed with the parent/guardian at the time of enrollment.

7.5 Physical Measures

Participants' height, weight and calculated BMI will be obtained at enrollment or from the clinical measurements collected at the visit. Pulse-rate and blood pressure will also be obtained at baseline from the clinical measurements. Height, weight, pulse rate, and blood pressure measurements will be performed by the study team if they are not otherwise available. In addition, the clinic baseline pain assessment will be recorded.

7.6 Needle Related Fear

Fear of having blood drawn has been shown to be predictive of vasovagal reactions in young blood donors.⁶ In blood donors fear was assessed using a global question. "How afraid are you of having blood drawn from your arm?" A similarly worded global question will be used to assess fear of vaccination. "How afraid are you of getting a vaccine (shot) in your arm?" Responses will be graded using a Likert scale which will have a range from 0, which indicates not at all afraid, to 5 which indicates extremely afraid. In

addition, we will use the American Psychiatric Association Severity Measure for Specific Phobia to assess needle related phobia. This assessment is a 10-item scale which specifically assesses phobia around blood, needles or injections in persons 11-17 years of age.^{6,19}

7.7 Anxiety

Prior to vaccination the study coordinator will have each subject complete a questionnaire to assess generalized anxiety using the Patient Reported Outcome Measurement Information System (PROMIS) Pediatric Anxiety Short Form v2.0 8a instrument for adolescents (11-17 years) to categorize their overall degree of anxiety.⁴⁰

Participants will also complete a questionnaire specifically designed for this study to measure state anxiety both prior to and 20 minutes following vaccination. State anxiety is defined as an unpleasant emotional arousal in face of threatening demands or dangers.^{41,42}

7.7.1 Risk Mitigation Procedure

If the subject scores into the severe category for anxiety measured from the PROMIS Pediatric Anxiety Short Form, the subject's score and answers will be shared with the subject's primary care physician.

7.8 Randomization

Participants will be randomized (1:1) to receive either Buzzy® and electronic game or the control using a permuted block randomization scheme. A minimum of 170 participants will be enrolled in the intervention group and 170 in the control group. The project statistician at Duke University will generate randomization schemes, which will be uploaded to REDCap. The randomization schedule will not be available to the study staff, so the next randomization allocation will not be known before randomization occurs. Following confirmation of study eligibility criteria during Visit 1, participant randomization will be through REDCap with treatment allocation recorded on the CRF.

7.8.1 Blinding

Study staff and subjects will not be blinded to treatment arm assignments.

7.9 Study Interventions

7.9.1 Buzzy® and Electronic Game Intervention

Participants randomized to Buzzy® and the electronic game will apply or have Buzzy® applied by a member of the study team. Buzzy® XL Healthcare Professional will be applied as described in the package insert on the deltoid vaccination site for 30-60 seconds. Then, the Buzzy® will be moved proximal to the injection site keeping Buzzy's® switch/head toward the brain or spine during injection. The procedures for applying Buzzy® are consistent with the procedures on the package insert (**Appendix A**). If vaccines are given in more than one arm, Buzzy® will be placed on both arms with the assistance of the study coordinator. Buzzy® will be removed from the vaccination site(s) following vaccination. The start and stop time of Buzzy® placement will be recorded. If more than one vaccination is given in a single arm only one Buzzy® device will be applied per package instructions.

For the electronic game, participants will be instructed to select a game from a prepopulated list of games on a tablet provided by the study team. The game will be played for a minimum of 3 to 5 minutes prior to vaccination, throughout the procedure and for a minimum of 1 minute and up to 15 minutes after vaccination.

Although preferable for participants to remain in the same exam room during the post-vaccination observation period, participants may have to shift rooms during the post-vaccination observation period. The participant will be provided with the guidance (derived from the Advisory Committee on Immunization Practices (ACIP) General Best Practices Guidelines for Immunization)²⁶ that they may choose to sit or lie down during the post-vaccination wait period. Movement from room to room or if the patient decides to stand should be noted by the study staff. No instruction will be provided to the participant regarding sitting or standing unless the participant starts to exhibit signs of presyncope.

7.9.2 Control Group

This intervention group will receive usual care during vaccination. Usual care will include not receiving the Buzzy® and electronic game combination intervention and will also consist of the patient waiting in the exam room for 20 minutes post-vaccination. The participant will also be provided with the ACIP guidance that they may choose to sit or lie down during the post-vaccination wait period. Although preferable for participants to remain in the same exam room during the post-vaccination observation period, participants may have to shift rooms during the post-vaccination observation period. Movement from room to room should be noted by the study staff.

7.10 Immunizations Administered During Visit

Vaccines received as part of usual care during the visit will be documented by the research staff. Documentation will include: product name and brand, lot number, site and date/time of vaccine administered during study participation.

7.11 Post Vaccination Pain Assessment

The Wong Baker Faces Pain Scale will be used to assess pain.⁴³ The Wong- Baker Faces Pain Scale scores pain on a 0-10 metric with 2 point intervals and shows a close linear relationship with visual analog pain scales across the ages from 11-17 years and is acceptable for use with younger adolescents as well. Pain will be assessed at 1 minute (up to 3 minutes) and at 10 minutes (up to 15 minutes) after vaccination for each arm in which a vaccine was received. The study coordinator will be responsible for recording pain scores after vaccination. The time for assessment will start after the last injection is received.

7.12 Presyncope and Syncope

At 15 minutes (up to 20 minutes) following vaccination, study participants will complete the BDRI. During the 15 minute (up to 20 minute) observation period, research staff

will also record any observed signs (pallor, sweating, facial flush or decreased interactivity) or spontaneous subject reports of symptoms of witnessed presyncope as described in Section 4.1. Subjects who developed post-vaccination syncope as described in Section 4.2 regardless of presyncope are classified as having syncope. Usual clinical care will be provided to any subject who develops presyncope or syncope.

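### The observation period that defines the primary endpoint has two stated lengths, and the symptom questionnaire may be completed up to 5 minutes before the longer one ends

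*Protocol*

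**What the plan says.** The primary outcome is the proportion with presyncope or syncope. Protocol 4.1 counts presyncope symptoms or signs that begin "during the post-vaccination observation period in the clinic", and Protocol 4.2 ties syncope to the same period. SAP 4.6 repeats both definitions. None of these sections gives the period a length.

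The length appears elsewhere, in two forms:

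- **20 minutes.** Protocol 5 states "Participants will be observed for 20 minutes following receipt of vaccines", and SAP 4.1 carries the same sentence. Protocol 7.9.2 and SAP 4.2 describe control patients "waiting in the exam room for 20 minutes post-vaccination".
- **15 minutes, extendable to 20.** Protocol 7.12, which governs how the endpoint is recorded, has staff note signs and spontaneous reports "During the 15 minute (up to 20 minute) observation period".

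On the self-report, Protocol 7.12 says "At 15 minutes (up to 20 minutes) following vaccination, study participants will complete the BDRI". The visit list in Protocol 7.1 gives the same range, and Table 1 simply shows 15 minutes. SAP 8.1 builds the endpoint from the modified BDRI or a witnessed event. The SAP gives no time for the BDRI and no rule for symptoms that start after it. Protocol 7.8.1 and SAP 4.5 state that staff and subjects are not blinded.

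**The concern.** The endpoint is defined by a period, and the plan does not fix that period. An event at minute 17 falls inside the period in Protocol 5. Under Protocol 7.12 it falls inside or outside depending on whether that participant's period ran to 15 or to 20 minutes.

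The more practical problem is capture. The BDRI is the only point at which every participant is asked about every symptom. Once it is completed, a new symptom becomes a case only if the adolescent mentions it or staff observe something. Staff know the allocation, so this route is less systematic and less objective than the form. One symptom at the lowest positive grade is enough to make a case under the primary definition, so a single late symptom can change a participant's status.

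At stake are some missed cases, a risk window that differs between participants, and a primary endpoint that two analysts could derive differently from the same records.

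**Working it through.** **1. Sections side by side**

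| Item | Source | Minutes |
|---|---|---|
| Observation, all participants | Protocol 5; SAP 4.1 | 20 |
| Wait, control arm | Protocol 7.9.2; SAP 4.2 | 20 |
| Wait, intervention arm | Protocol 7.9.1; SAP 4.2 | period named, no number |
| Observation for recording signs and spontaneous reports | Protocol 7.12 | 15, up to 20 |
| BDRI completion | Protocol 7.1, 7.12 | 15, up to 20 |
| State anxiety form | Protocol 7.1 | 20, up to 25 |
| Acceptability form | Protocol 7.1 | 20, up to 30 |

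The largest gap between the BDRI and the end of a 20-minute period is 20 − 15 = 5 minutes. The start of the clock is also open. Protocol 7.11 starts it after the last injection for pain, but Protocol 7.12 says only that timing follows vaccination.

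**2. The plan's own power figure**

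Inputs from Protocol 8.1: 160 per group, 25% v 12.5%, two-sided alpha 0.05, chi-square test.

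Power = Φ[(d − 1.96·SE0)/SE1], with SE0 = √(2·p̄(1−p̄)/n) and SE1 = √((p1(1−p1) + p2(1−p2))/n).

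- d = 0.125 and p̄ = 0.1875
- SE0 = √(2 × 0.1875 × 0.8125/160) = 0.04364
- SE1 = √((0.1875 + 0.109375)/160) = 0.04307
- (0.125 − 0.08553)/0.04307 = 0.916, and Φ = 0.820

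This reproduces the stated 82.0%. The sample-size calculation is not in error.

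**3. Equal loss in both arms**

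Suppose a share m of cases has its only qualifying symptom or sign after the BDRI and is not captured. Each rate is then multiplied by (1 − m). The documents give no m for presyncope. For scale, the background section of the protocol says 89% of syncope reports to VAERS occurred within 15 minutes, which leaves 1 − 0.89 = 11% later.

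| m (assumed) | Control | Intervention | Relative risk | Power at 160 per group | n per group for 82% |
|---|---|---|---|---|---|
| 0 | 25% | 12.5% | 0.50 | 82.0% | 160 |
| 2% | 24.5% | 12.25% | 0.50 | 81.1% | 164 |
| 5% | 23.75% | 11.875% | 0.50 | 79.6% | 171 |
| 11% | 22.25% | 11.125% | 0.50 | 76.3% | 185 |

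**4. Worst case: loss in one arm only**

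Take true rates of 25% in both arms, with late cases lost in one arm.

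- m = 11%: 0.25 × 0.89 = 22.25%. The comparison of 25% v 22.25% rejects in 8.9% of trials.
- m = 5%: 0.25 × 0.95 = 23.75%. The comparison rejects in 5.8% of trials.

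These show only what would follow if timing split completely by arm. The plan does not set up such a split.

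**The case against.** The best defence is that the protocol writes all its assessment times as a target with an upper limit: 1 (up to 3), 10 (up to 15), 20 (up to 25). On that reading, 15 (up to 20) is a tolerance inside a 20-minute stay. It never exceeds Protocol 5, and a witnessed event at minute 17 can still be counted. This is a fair reading of the BDRI time. It does not settle the case definition, because Protocol 7.12 attaches the range to the observation period itself. Nor does it close the gap in self-report after a BDRI completed at minute 15.

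A second defence is that few cases would be lost. A participant is missed only if none of the 12 symptoms and no sign began before the BDRI, and nothing later was volunteered or seen. This stands, and it is why the effect is probably small.

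A reader might infer that the two arms have different windows, because the explicit wait is written for controls and the intervention text gives no number. The documents do not support that. Protocol 5 and SAP 4.1 apply 20 minutes to all participants. The anxiety and acceptability forms keep both arms in clinic to at least minute 20. Protocol 7.9.1 refers to the same observation period without repeating its length. The game's upper limit of 15 minutes coincides with the earliest BDRI time, so it need not delay the form in one arm.

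A reader might also infer that BDRI completion time is not recorded. The case report forms are not among the documents, so this is unknown.

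**Conclusion.** The inconsistency is real and lies within the primary endpoint, but its likely effect is modest: minor to moderate. The same ranges apply to both arms, so the expected result is a small loss of events and power with no shift in the relative risk. Power would fall from 82.0% to between 81.1% and 76.3% for assumed losses of 2% to 11%.

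The range rests on these assumptions:

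- The planned 25% and 12.5% refer to the full 20 minutes. The documents do not say which window they cover.
- The loss is proportionally equal in the two arms.
- The 11% end is a ceiling. It concerns syncope reports rather than presyncope, has no upper time limit, and would require every late case to be missed.

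Bias between arms would need BDRI timing or staff recording to differ by arm. That is possible because the trial is open label, but no section prescribes it. The 8.9% rejection rate is a worst-case illustration and should not be read as the trial's type I error.

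**What to change.** Reconcile Protocol 4.1, 4.2, 5, 7.1, 7.9.1, 7.9.2 and 7.12, and SAP 4.1, 4.2 and 4.6, as follows:

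1. State one endpoint window with a fixed length and a stated start point, identical in both arms. The length is for the sponsor to choose.
2. Have the BDRI completed at the close of that window, and word it to ask about the whole of it.
3. Record the BDRI completion time if the form does not already do so, and tabulate it by arm.

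**Cost.** The change is mainly to wording in two documents. If the window is 20 minutes, one form moves by at most about 5 minutes in a visit that already runs past minute 20. Its order relative to the state anxiety and acceptability forms must then be set, since both fall due from minute 20. Keeping the BDRI first would preserve the present sequence. No extra visit or participants are needed, whereas holding 82% power under the assumed losses would take 4, 11 or 25 more per group (164, 171 or 185, less 160).
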